12.2 Variables

Data file record_id & patient_ display_id_full	Notes	Variable name	Variable label	Variable level	Nominal values
event_evaluation	no report	AESTDT	Onset date	date	n.a.
event_evaluation	no report	AERELSET	Adverse Event is relevant for SADE endpoint	nominal	 Yes  No

Data file record_id & patient_ display_id_full	Notes	Variable name	Variable label	Variable level	Nominal values
data_SAR	no report	date_implantation_SAR	Date of implantation	date	n.a.
	no report	date_censoring_SAR	Date of censoring (latest date of AE onset, AE resolution, implantation, PHD, 3m FU, 6m FU, 12m FU, or date of study termination)	date	n.a.
	no report	date_1stSADE_corfamily_SAR ¹⁰⁶	Date of first Cor family related SADE	date	n.a.
	descriptive and 95% CI, Kaplan Meier analysis	any_SADE_corfamily_SAR ¹⁰⁷	Any Cor family related SADE	nominal	 Yes  No
		days_impl_1stSADE_ corfamily_SAR ¹⁰⁸	Days from implantation to first Cor-family related SADE or censoring	date	n.a.

12.3 Treatment of Missing and Spurious Data

See general definitions in chapter 5.4.

12.4 Exclusion of Particular Information

See general definitions in chapter 5.5.

12.5 Descriptive Analyses

See general definitions in chapter 5.1 and notes previous variable tables. A Kaplan-Meier survival curve has to be reported.

12.6 Hypotheses & Statistical Tests

CIP chapter 7.2.2.1 Secondary endpoint 1: Kaplan-Meier estimate for the Cor Family related SADE-free rate

The Kaplan-Meier method will be applied to estimate the 3-month SADE-free rate at 92 days after implantation (sensitivity analysis of the primary endpoint) and the 12-month SADE-free rate at 365 days after implantation. Thereby all patients will be included in the analysis.

The pointwise 95% confidence interval has to be calculated via the loglog transformation.

13 Sec. Endpoint 2: Automatic LV VectorOpt test (CRT only)

13.1 Analysis set

All analyses are performed for the CRT analysis set.¹⁰⁹

13.2 Variables

CIP chapter 7.2.2.2 Secondary endpoint 2: Automatic LV VectorOpt test (CRT only)

At Pre-Hospital Discharge or at the latest at 3-month follow-up, the following endpoints related to the automatic LV VectorOpt test will be assessed:

- a. time needed to perform the LV threshold measurement manually
- b. time needed to perform the LV threshold measurement automatically
- c. investigator appraisal (score) of RV-LV conduction time test
- d. investigator appraisal (score) of intuitiveness of the threshold test
- e. investigator appraisal (score) of ease to find the best LV pacing configuration
- f. investigator appraisal (score) of overall handling of the Auto LV VectorOpt feature
- g. investigator agreement (score) to different statements relating to programmer-based LV vector optimization

Data file identifier patient_display_id_full	Notes	Variable name	Variable label	Variable level	Nominal values
auto_lv_vectoropt	descriptive (a)	DULVTHMT	Time needed to run the LV threshold measurement manually	scale hh:mm:ss has to be converted to min	n.a.
	descriptive (b)*	DULVTHAT	Time needed to run the LV threshold measurement automatically (same subset of vectors)	scale hh:mm:ss has to be converted to min	n.a.

Data file identifier patient_display_id_full	Notes	Variable name	Variable label	Variable level	Nominal values
auto_lv_vectoropt	descriptive (c)	DURVLVAS	Do you consider the RV-LV conduction time test helpful?	nominal	 Yes  No  Not done
	descriptive (d)	DUITHTAS	Intuitiveness of the threshold test	nominal	 Very intuitive  Intuitiv  Adequate  Difficult  Very difficult
	descriptive (e)	DUBLVPAS	Ease to find the best LV pacing configuration	nominal	 Very easy  Easy  Adequate  Difficult  Very difficult
	descriptive (f)	DULVVOAS	Overall Handling assessment of the Auto LV VectorOpt feature	nominal	 Very good  Good  Adequate  Poor  Very poor
	descriptive (g)	DUINVAS01	The parameters RV-LV conduction time, PNS threshold and impact on device longevity (pacing threshold) provide a good decision basis and are sufficient for a clinically acceptable LV vector optimization	nominal	 Strongly agree  Somewhat agree  Neither agree nor disagree  Somewhat disagree  Strongly disagree
	descriptive (g)	DUINVAS02	Auto LV VectorOpt is an ergonomic tool for informed decision making and recommending which vector to select	nominal	 Strongly agree  Somewhat agree  Neither agree nor disagree  Somewhat disagree  Strongly disagree
	descriptive (g)	DUINVAS03	The automatic measurement process simplifies the process of finding a suitable LV pacing vector for CRT	nominal	 Strongly agree  Somewhat agree  Neither agree nor disagree  Somewhat disagree  Strongly disagree

Data file, identifier patient_display_id_full	Notes	Variable name	Variable label	Variable level	Nominal values
auto_lv_vectoropt	case listings	COITHTAS	Please specify intuitiveness of test	text	n.a.
	case listings	COBLVPAS	Please specify ease of finding LV pacing configuration	text	n.a.
	case listings	COLVVOAS	Please specify overall assessment	text	n.a.

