1. A Kaplan-Meier estimate for the SADE-free rate at 3 and 12 months will be performed as a sensitivity analysis for the primary endpoint.
2. The Automatic LV VectorOpt test will be evaluated with regard to time savings, usability and acceptance criteria. This test was chosen as endpoint because it is a new feature that consists in a further development of the already known manual LV VectorOpt test which was investigated in the BIO|MASTER.Edora Family study.
3. The CRT AutoAdapt feature will be evaluated with regard to its programming, the behavior of the algorithm, usability and acceptance criteria. While CRT AutoAdapt aims at improving hemodynamics, it is not expected that significant effects on hemodynamics can be detected due to the small sample size and relatively short duration of this investigation. However, data on the functionality and acceptance of the feature contribute to this secondary endpoint that was chosen in order to gain more insight in the clinical use of this new feature.

¹ MEDDEV 2.7/1 Rev. 4

² MEDDEV.2.12/2 rev.2: 2012 Guidelines on Post Market Clinical Follow-up

BIOTRONIK SE & Co.KG // BIO|MASTER.Cor Family

Automatic LV VectorOpt and CRT AutoAdapt are new features that were implemented for the first time in BIOTRONIK devices and therefore chosen as secondary endpoints.

Another focus of the study is the data collection for the Plexa S DX lead with DF4 connection. For this reason data of interest are recorded to assess the atrial sensing performance and lead related adverse events but also the handling assessment during the implantation.

The product design of the DF4 variant of Plexa S DX is identical to the Plexa S DX DF-1 lead, except for the connector. In the BIO|MASTER.Ilivia Family/Plexa study, 27 Plexa S DX DF-1 leads were analyzed and already provided enough clinical data for the safety and efficacy of the DX lead variants²⁸. Therefore, 30 Plexa S DX leads with DF4 connection are considered to be sufficient for the evaluation in this study.

The decision to include the Plexa S DX lead into the Master Study for the Cor Family devices is based on the fact that Acticor/Rivacor VR-T DX is the only device on the market that is compatible with this new DX lead with DF4 connection. Thus, the requirements for a PMCF for both devices were combined in one study.

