8.1.3 Selection of measurements for endpoints

For the primary endpoint, the SADE-free rate will be assessed by collecting and evaluating adverse events until the 3-month follow-up. This assessment was chosen to comply with preceding studies regarding result consistence and comparability and regarding acceptance by regulatory authorities outside Europe. As one objective of secondary endpoint 1 is a sensitivity analysis for the primary endpoint, the assessment of data – collection and evaluation of adverse events within a pre-specified timeframe – must be consistent between these endpoints. Secondary endpoint 2 aims at evaluating the Automatic LV VectorOpt test feature. The measurements were selected in order to collect data to support the intended claims for this feature (see section 7.3). As the CRT AutoAdapt feature (secondary endpoint 3) will be turned on at pre-hospital discharge (if applicable), its acceptance and performance is assessable through the measurement of device parameters – such as reprogramming, percentage CRT pacing etc. – at subsequent follow-ups. The percentage of CRT pacing is a crucial parameter for the effectiveness of cardiac resynchronization therapy. Evaluation of the CRT AutoAdapt performance using CRT response parameters is not feasible due to the small sample size of this study.

For both endpoints, Auto LV VectorOpt and CRT AutoAdapt, usability, user acceptance, clinical acceptability and overall assessments by the investigator play an important role, also with respect to validation of claims. However, these characteristics are very subjective, hardly measurable through device parameters, and hence commonly assessed by questionnaires. Therefore, scores with five categories (e.g. "Very good/good/adequate/poor/very poor") were chosen to rate these properties. Comment fields will be used to justify the chosen category.

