8.1.4.8 Automatic LV VectorOpt test

The Automatic LV VectorOpt test has to be mandatorily performed in CRT-D patients. It is recommended to perform the test at pre-hospital discharge, but testing at implantation or at 3-month follow-up (if not done before) is also acceptable.

It is recommended to perform the measurement of RV/LV conduction times at the beginning of the test to facilitate the selection of vectors that are to be measured. In order to allow for a comparison of manual and automatic testing, the investigator is asked to perform the manual LV VectorOpt test first, the choice of at least 3 vectors being at the investigator's discretion. After that the automatic LV VectorOpt test shall be performed for the same subset of vectors. Finally, the automatic LV VectorOpt test will be performed for all 20 available vectors. Alternatively, a different subset of vectors at the investigator's discretion may be chosen for the automatic LV VectorOpt test.

Finally, the PNS thresholds shall be measured manually for a selection of vectors at the investigator's discretion.

The documentation in the eCRF will comprise of the following items:

- Did you perform the RV-LV conduction time test (RVp-LVs, RVs-LVs or both)? [Yes/No]
- Time needed to run the LV threshold measurement manually (and indication of the number of vectors tested)
- Time needed to run the Auto LV threshold measurement of the same subset of vectors (that were selected for the manual test)
- Time needed to run Auto LV threshold measurement (using all 20 vectors or for the selected vectors)
- Listing of pacing vectors that were tested during the automatic and/or manual procedure [Multiple choice]
- Number of vectors for which the PNS threshold was measured

- Values for sensing amplitude, pacing impedance, pacing threshold and PNS threshold of the finally programmed pacing vector
- Assessment of the Auto LV VectorOpt test by the investigator:
 - Do you consider the RV-LV conduction time test helpful? [Yes/No/Not done]
 - How did you preselect the pacing vectors that were measured automatically?
 - Intuitiveness of the threshold test (Score: "Very intuitive/intuitive/adequate/poor/very poor")
 - Ease to find the best LV pacing configuration (Score: "Very easy/easy/adequate/difficult/very difficult")
 - Did you program the permanent pacing vector directly from the result table of the Auto LVVO? [Yes/No]

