Data file identifier patient_display_id_full	Notes	Variable name	Variable label	Variable level	Nominal values
auto_lv_vectoropt	descriptive	DULVVT	Automatic LV VectorOpt test done at	nominal	 PHD  Implantation  3-month Follow-Up
	descriptive	DURVLVCT	Did you perform the RV-LV conduction time test?		 Yes, only RVp-LVs  Yes, only RVs-LVs  Yes, both: RVp-LVs and RVs-LVs  No
	case listings for COLVVTND not missing	COLVVTND	Please specify not performing Auto LVVectorOpt test	text	n.a.

Automatic LV VectorOpt Test / Manual and automatic testing of pacing vectors

Data file identifier patient_display_id_full	Notes	Variable name	Variable label	Variable level	Nominal values
auto_lv_vectoropt	descriptive	DUNVST	Number of vectors selected for testing (minimum 3)	ordinal	...
	descriptive	DUBOTHM	Were both measurements performed with the same subset of vectors?		 Yes  No
	case listings for DUBOTHM = No	COBOTHM	Please specify difference of tested vectors	text	n.a.

Automatic LV VectorOpt Test / Manual and automatic testing of pacing vectors / HF-T QP

Data file identifier patient_display_id_full	Notes	Variable name	Variable label	Variable level	Nominal values
auto_lv_vectoropt	descr.	DULVVTFO1 with "not done" to be analyzed as missing data	Was the automatic LV VectorOpt test performed for all 20 vectors	nominal	 Yes  No, other number tested  Not done
	descr.	DUNVST01	NEW: Other number of vectors tested <>20	ordinal	...
	descr.	DULVTHAT01	Time needed to run Auto LV threshold measurement for 20 or selected vectors	scale hh:mm:ss has to be converted to min	n.a.

Automatic LV VectorOpt Test / Manual and automatic testing of pacing vectors / HF-T

Data file identifier patient_display_id_full	Notes	Variable name	Variable label	Variable level	Nominal values
auto_lv_vectoropt	descr.	DULVVTFO2 with "not done" to be analyzed as missing data	Was the automatic LV VectorOpt test performed for all 5 vectors	nominal	 Yes  No, other number tested  Not done
	descr.	DUNVST02	NEW: Other number of vectors tested <>5	ordinal	...
	descr.	DULVTHAT02	Time needed to run Auto LV threshold measurement for 5 or selected vectors	scale hh:mm:ss has to be converted to min	n.a.

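### Secondary endpoint 2 collects manual and automatic test times as within-patient pairs, but the visible SAP summarises them only separately, so the spread, interval and median of the time saving cannot be recovered

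*SAP*

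**What the plan says.** **Purpose.** Protocol 5.3 says the automatic test is to be "evaluated with regard to time savings, usability and acceptance criteria". On the measurements for this endpoint, Protocol 8.1.3 adds: "The measurements were selected in order to collect data to support the intended claims for this feature".

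**Design.** Protocol 8.1.4.8 states: "In order to allow for a comparison of manual and automatic testing, the investigator is asked to perform the manual LV VectorOpt test first". The investigator chooses at least 3 vectors. The protocol continues: "After that the automatic LV VectorOpt test shall be performed for the same subset of vectors". Each patient therefore provides a pair of times on a common set of vectors.

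**Endpoint definition.** Protocol 7.2.2.2 lists the manual time (item a) and the automatic time (item b) as separate items. It does not list a difference.

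**Analysis.** SAP 13.2 carries these over as two scale variables. DULVTHMT is labelled "Time needed to run the LV threshold measurement manually"; DULVTHAT is the automatic time, labelled as referring to the same vector subset. Both are marked descriptive only. Under SAP 5.1 that means the usual summary statistics for a continuous variable, without an interval. SAP 13.5 refers back to 5.1 and the table notes, and SAP 13.6 specifies no hypotheses.

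**Check on the pairing.** SAP 9.2.6 tabulates DUBOTHM ("Were both measurements performed with the same subset of vectors") and lists the cases answered No, with the difference described. It also records DUNVST, the number of vectors selected.

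**The concern.** A time saving is a contrast, and the protocol asks for both tests in the same patient so that the contrast can be made. The visible SAP stops one step short by describing each time on its own.

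Three things follow.

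- A reader of the report cannot tell how variable or how precisely estimated the saving is, what the median saving is, or in what share of patients the automatic test was faster.
- SAP 5.4 imputes nothing and the standard table for scale data works on non-missing values. If some patients have only one of the two times, the two summaries describe different patients, and even the subtracted mean is no longer a within-patient saving.
- The number of vectors is left to the investigator. The full set is 20 for HF-T QP and 5 for HF-T (SAP 9.2.6). Testing more vectors plausibly lengthens both tests, so a positive within-patient correlation is likely, and separate summaries lose that information.

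At stake is how well the study can support whatever is claimed about speed. The safety conclusion is not involved.

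**Working it through.** **The plan's own figures.** No sample size or precision is stated for secondary endpoint 2. The only sized analysis is the primary one. Its 114 evaluable patients reproduce with an exact binomial test (90% against 98%, two-sided 5%, power at least 95% at that and every larger size tested, up to 400): power is 97.3% at 114 and 92.3% at 113. Then 114 / (1 - 0.10) = 126.7, rounded up to 127. This does not bear on the timing endpoint.

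**Number of pairs.** Protocol 8.2.4 plans 15 + 30 + 15 + 15 + 52 = 127 devices. The CRT devices are 15 HF-T + 52 HF-T QP = 67, which is the maximum number of pairs with no loss.

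**What the two summaries determine.** Let M be manual time and A automatic time, with SDs s1 and s2 and within-patient correlation r.

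- Mean saving: mean(M - A) = mean(M) - mean(A), provided the same patients supply both. This is recoverable.
- SD of the saving: sqrt(s1² + s2² - 2·r·s1·s2). This needs r, which neither summary contains.
- Median saving and share with M - A > 0: these depend on the joint distribution and are not recoverable.

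**Size of the gap.** The documents give no s1, s2 or r, so these are assumptions. With s1 = s2 = s, the 95% half-width for the mean saving is t(0.975, n-1) · s · sqrt(2(1 - r)/n), in units of s:

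| r | n = 67 | n = 60 (about 10% loss, assumed) |
|---|---|---|
| 0 | 0.345 | 0.365 |
| 0.3 | 0.289 | 0.306 |
| 0.5 | 0.244 | 0.258 |
| 0.7 | 0.189 | 0.200 |
| 0.9 | 0.109 | 0.116 |

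The same pair of marginal summaries fits every row in a column. At n = 67 that is a range of 0.345 / 0.109 = 3.2-fold.

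**Illustration in minutes (invented values).** Take manual mean 5 (SD 3), automatic mean 3 (SD 2) and n = 67. The mean saving is 2 minutes.

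- With r = 0, the SD of the saving is sqrt(9 + 4) = 3.61 and the 95% CI is 1.12 to 2.88.
- With r = 0.9, the SD is sqrt(13 - 10.8) = 1.48 and the 95% CI is 1.64 to 2.36.

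The planned tables would look identical in the two cases.

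**The case against.** The strongest reply is that the SAP does what the endpoint definition asks. Protocol 7.2.2.2 names two times and no difference, and SAP 13.2 reports those two times. The saving appears in the justification. All analyses other than the primary are exploratory (SAP 5.3), and nothing in the SAP bars a later subtraction. This is fair as far as it goes: the SAP does not contradict the endpoint list. But Protocol 8.1.4.8 says why both tests are done in each patient, and that purpose is comparative. A difference added later would not be specified in advance.

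Three stronger readings are tempting, and the documents do not support them.

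- *That the plan gives no estimate of the saving at all.* With complete pairs, the difference of the two reported means is the mean saving. What is missing is its spread and interval, the median saving and the share of patients who saved time.
- *That the plan loses a definite amount of precision.* A paired interval is 16% to 45% narrower than an unpaired one (0.342 SD at n = 67) for r between 0.3 and 0.7. The SAP plans no unpaired interval, so this is not a loss under the current plan.
- *That unmatched vector sets are certainly mixed in.* The automatic time is labelled as referring to the same subset, and SAP 9.2.6 tabulates mismatches and lists them case by case. The asterisk at item (b) has no readable note, and SAP 13.3 points to a rule for the manual time that cannot be read either. Either may already restrict the pairs. It can only be said that no restriction is visible in SAP 13.2.

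**Conclusion.** The point holds as a missing within-patient summary. The protocol's purpose and design are comparative and paired, while the visible SAP reports only two separate distributions. These fix the mean saving when the same patients supply both times, but they leave its 95% half-width undetermined between 0.345 and 0.109 SD. That range assumes equal SDs, 67 complete pairs and correlations from 0 to 0.9, since the documents give none of these.

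Two limits apply. The note at item (b) and the rule behind SAP 13.3 are unreadable, so a hidden instruction cannot be excluded. Also, the protocol asks for the manual test first in every patient, so even a paired difference mixes method with order, which an interval does not remove.

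A reader might infer that this weakens the study's conclusion or calls for a hypothesis test. It does neither. Protocol 11.5 makes pass or fail depend on the primary hypothesis alone, and an estimate with an interval is enough for an exploratory endpoint. The contents of the claims table in Protocol 7.3 are not visible, so it is unknown whether a quantified saving is to be claimed. This is a free improvement to an exploratory secondary endpoint.

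**What to change.** In SAP 13.2:

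1. Add a derived variable, DULVTHMT minus DULVTHAT in minutes, for patients in the CRT analysis set with both times and DUBOTHM = Yes.
2. Add a per-vector version, divided by DUNVST, because the number of vectors varies between patients.
3. Report the number of pairs, the mean and median difference with 95% confidence intervals, and the share of patients with a saving above 0. Label them exploratory, with no test and no multiplicity adjustment.
4. State that the manual test comes first by design, so order may affect the difference.
5. Keep the two existing summaries. If the note at item (b) or the rule behind SAP 13.3 already handles unmatched subsets, align the new variable with it.

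The cost is one derivation (with its per-vector form) and one table. All four source variables are already collected.

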13.3 Treatment of Missing and Spurious Data

See general definitions in chapter 5.4.

See time needed to perform the LV threshold measurement manually.

13.4 Exclusion of Particular Information

See general definitions in chapter 5.5.

13.5 Descriptive Analyses

See general definitions in chapter 5.1 and notes previous variable tables.

13.6 Hypotheses & Statistical Tests

There are no pre-specified hypotheses.

14 Sec. Endpoint 3: CRT AutoAdapt feature (CRT only)

14.1 Analysis set

All analyses are performed for the CRT AutoAdapt analysis set.¹¹⁰

14.2 Variables

CIP chapter 7.2.2.2 Secondary endpoint 3: CRT AutoAdapt (CRT only)

At the 3-month follow-up the CRT AutoAdapt feature will be assessed with regard to the following endpoints:

- a. percentage of CRT pacing since last follow-up
- b. percentage of adaptive BiV pacing since last follow-up
- c. percentage of programmed BiV pacing since last follow-up
- d. percentage of adaptive LV pacing since last follow-up
- e. mean adapted AV delay after pace/sense
- f. rate of patients in whom the programming of CRT AutoAdapt is maintained beyond the 3-month follow-up
- g. reasons for deactivation of CRT AutoAdapt
- h. investigator appraisal (score) of programmability
- i. investigator appraisal (score) of clinical acceptability
- j. investigator appraisal (score) of overall assessment of the CRT AutoAdapt feature

Lead measurements / Percentage of CRT pacing since last follow-up

The following analyses have to be performed for the data of the 3m follow-up¹¹¹.

Data file, identifier PRVISIT & patient_display_id_full	Notes	Variable name	Variable label	Variable level	Nominal values
lead_measurement	no report	PRVISIT	Visit	nominal	 3m Follow-up ...
	descriptive (a)	DUMCRTP	Mean CRT pacing since last follow-up [%]	scale	n.a.
	descriptive (e)	DUAVDAPO	Optimized AV delay after pace [ms]	scale	n.a.
	descriptive (e)	DUAVDASO	Optimized AV delay after sense [ms]	scale	n.a.
	descriptive (f) 2x2 table dis_DUAUAON x m03_DUAUAON	dis_DUAUAON ¹¹² m03_DUAUAON	PHD: CRT AutoAdapt "ON" M03: CRT AutoAdapt "ON"	nominal	 Yes  No

Data file patient_ display_id_full	Notes	Variable name	Variable label	Variable level	Nominal values
follow_up_3m	descriptive	DUAUAON	NEW: CRT AutoAdapt "ON" at the end of the 3mo FU	nominal	 Yes  No
	descriptive for DUAUAON = No (g)	COAUAOFF	Please specify why CRT AutoAdapt "OFF" or "AVAdapt"	nominal	 Patient has chronic complete AV block (contraindication)  Other
	descriptive (h)	DUPRGAS	Programmability	ordinal	 Very easy  Easy  Adequate  Poor  Very poor
	descriptive(i)	DUALGRAS	Clinical acceptability of the algorithm's decision	ordinal	 Very good  Good  Adequate  Poor  Very poor
	descriptive (j)	DUAUAOAS	Overall assessment of the CRT AutoAdapt feature	ordinal	 Very good  Good  Adequate  Poor  Very poor

Data file patient_ display_id_full	Notes	Variable name	Variable label	Variable level	Nominal values
follow_up_3m	case listings for COAUAOFF = Other	COAUAOOTH	Other Reason for CRT AutoAdapt OFF	text	n.a.
	case listings for poor assessments	COPRGAS	Comment on programmability	text	n.a.
		COALGRAS	comment on clinical acceptability of the algorithm's decision	text	n.a.
		COAUAOAS	comment on overall assessment	text	n.a.

Home Monitoring Data

Data file, identifier date & patient_ display_id_full	Notes	Variable name	Variable label	Variable level	Nominal values
V_TACHY (CDW datamart)	descriptive (b)	HMADAPBIVP	Adaptive BiV pacing since last follow-up [%]	metric	n.a.
	descriptive (c)	HMPRGBIVP	Programmed BiV pacing since last follow-up [%]	metric	n.a.
	descriptive (d)	HMADAPLVIP	Adaptive LV pacing since last follow-up [%]	metric	n.a.

